6.4 Selection of Study Sites and Subjects

Pieces will screen electronic health records of participating healthcare systems to detect patients with a triad of CKD, diabetes and hypertension according to established inclusion criteria for the study. (see *figure 6.3.1 Detection for CKD, Diabetes and Hypertension*)

The candidate cohort of potential sites will then be randomized to active intervention (collaborative care model enhanced by Pieces) or control group (standard of care) (see *figure 6.3.2 Detection CKD, Diabetes and Hypertension*).

Within clinics randomized to intervention, Pieces will confirm patients meet inclusion criteria. (see *figure 6.3.3 Patient Identification Workflow*).

[figure not shown]

Figure 6.4.1 Detection for CKD, Diabetes and Hypertension

ICD-Pieces Implementation Work Flow

[figure not shown]

Figure 6.4.2 Detection CKD, Diabetes and Hypertension

ICD-Pieces Patient Identification Work Flow

[figure not shown]

Figure 6.4.3 Patient Identification Workflow

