5.4 Treatment Assignment Procedures

This is a prospective stratified cluster randomized trial. Primary care practices will be stratified by healthcare system and randomly allocated to active intervention or control using standard

medical care using a randomized permutation block within stratum. There will be no masking of sites randomized to active intervention.

Practitioners and/or patients can choose to withdraw for the study at any time. They can choose not to follow the intervention model (any or all of the components or tools of care). Patient can request their data be not included for analysis of outcomes.

The study can be terminated by the DSMB for various reasons including concerns about adherence to protocols, study enrollment or patient safety.

6. Study Interventions

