6.3 Practice Facilitator

A key component of the collaborative model of care for the intervention group is the introduction of practice facilitators. In order to maximize the successful implementation of care in the intervention group the role training of the practice facilitator will be standardized across sites. We will use a curriculum developed following principles detailed in the Practice Facilitation Handbook from the Agency for Healthcare Research and Quality and especially adapted for ICD-PIECES.^[89] We have two content experts that will lead these efforts. [name] from NIDDK has developed educational programs which have been successfully used by NKDEP to successfully train healthcare professionals to care for thousands of patients who have CKD, diabetes and hypertension. [name] from SUNY directs a training program at SUNY for practice facilitators working in primary care practices.

There will be an initial on-site course for practice facilitators led by [name] and [name]. After that initial meeting ICD-PIECES will continue to provide scheduled events by teleconference, written material and webinars to disseminate study relevant material to practice facilitators. All practice facilitators will also participate in regularly scheduled calls to review study progress. It is anticipated that these call will be at least weekly early in the study with additional calls and site visits to each site over the duration of the study.

Practice facilitators may defer in professional qualifications among the different healthcare sites. Practice facilitators will have some clearly defined responsibilities including the following:

- Receive initial and on-going training from the study team about the study, study protocol and proposed intervention
- Ensure training of designated clinic staff on clinic level activities and expectations
- Ensure necessary participation of designated clinic staff in CKD, diabetes, and hypertension care

- Coordinates with study clinic staff to ensure the following activities:
 - List of eligible patients scheduled for clinic visit weekly are received through the EHR weekly
 - Site-specific enrollment protocol are activated for eligible patients
 - Smart/Order set in the EHR are triggered for enrolled patients
 - Holds weekly conference calls with clinic representatives to answer any questions and monitor enrollment number for each clinic

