- In-person visit to observe processes of enrollment and Smart/Order set trigger and other intervention activities
- Provides regular update to the site PI and monthly update to the study team on enrollment number, performance of study clinic and on-going challenges

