6.5 Implementation Collaborative Model of Care

The interventions selected for this pragmatic trial are supported by prior studies, clinical evidence and/or guidelines for treatment of CKD, diabetes and hypertension.^[5,25,24,65,67-71,31,34,11] Specific interventions include maintaining blood pressure less than 140/90mmHg, use of angiotensin-converting enzyme inhibitors (ACEI) or angiotensin receptor blockers (ARB), treatment with statins, aiming for hemoglobin A1C at the recommended target for coexisting

comorbidities, and avoiding nephrotoxic medications including non-steroidal anti-inflammatory drugs (NSAIDS). Other interventions will include education on CKD for both primary care providers and for patients using material prepared by NKDEP. Material on lifestyle modification and immunizations will also be included. (see figure 6.5.1)

After a patient is enrolled, the primary care practitioner activates the CKD, diabetes and hypertension collaborative model of care. The primary care practitioner will also have the option to activate smart forms already constructed and available from our team (see appendix section) from the electronic health record. Primary care practitioners will have the option to initiate protocols for CKD management, hypertension management, lipid and diabetes management. Protocols can be initiated via smartsets in the EHR. (see figures 6.5.2 *Initiation of Protocol from SmartSets and Links to SmartSets*). The specific and detailed protocols for hypertension management and diabetes/lipid management are included in appendices.

ICD-Pieces Patient Care Work Flow

[figure not shown]

Figure 6.5.1

Initiate Protocol from SmartSets

- From the SmartSet, the provider can place all 3 initiate orders at once, in a Future status

[figure not shown]

Figure 6.5.2 Initiation of Protocol from SmartSets

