7.1 Screening

Potential study participants from each healthcare system followed in primary care clinics randomized to the study will be screened for inclusion according to the pre-established criteria for CKD, diabetes and hypertension (see section 5.1) and as illustrated in figure 6.3.1

There are no plans to obtain individual informed consent for patients screened or randomized in the study. (see section 14.3) Information about the study will be available to all patients in participating clinics and who have the triad of CKD, diabetes and hypertension. There will be an opt-out opportunity from the interventions or from use of information from any patient who requests their data not to be used for analysis.

Screening of participants will occur at an initial stage to identify a candidate cohort of patients in various eligible clinics (see figure 6.3.2). Patients who do not fulfill required diagnostic criteria on initial review and require a separate determination to confirm any of the three diagnosis will be rescreened at the time of a future visit (figure 6.3.3)

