13.1 Development of MOP and Training

The main thrust of our quality control and assurance program is to prepare a comprehensive manual of operation with sections specific to each study site and train study site staff in its operations. Study site personnel to be trained are the site PI, the Practice Facilitator and Primary Care Providers at each clinic. The site PI will provide oversight to the conduct of the study at their institution, responsible for recruitment of appropriate staff to serve as Practice Facilitator and engaging PCPs in the clinics randomized to study group. The Practice Facilitator will receive the list of eligible patients along with their PCPs to ensure that the patients are enrolled into the study and provided recommended care through triggering of the Smart Set and following protocol. The PCPs will be primarily responsible for providing recommended care to their eligible patients and determine the level of care for each patient. Training will be provided to these staff by members in person meetings, web-based training and the manual of operation that outlines their expected roles, clinical workflow, opt-out consent and patient follow up. A refresher training course will be provided every three months to ensure compliance with the manual of operations.

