As a condition of the data use agreements signed with ProHealth Physicians, individual elements of the Safe Harbor elements of PHI are encrypted before transmission until they are needed for final data sets linkages for outcome standardization to maximize patient privacy and minimize data loss risk. As a result the data base of candidate and confirmed patients will be mirrored on the ProHealth Corporate Data ware house to allow subsequent on premises identification and generation of worklists.

Data transfers from Pieces system to participating sites

Standardized worklists that represent patients will be transmitted to the clinical sites. Patients with a candidate status and upcoming appointments in the subsequent week will be reported to the practice facilitator for additional follow up confirmatory testing to be arranged. An additional report on confirmed patients with planned visits in the coming week will also be transmitted to the sites. Additional reports on candidate or confirmed patients presenting in the prior week, not reported on the prior report due to new interval data or scheduling changes since the time of the prior report will also be transmitted. Where these data transfers can trigger additional provider notification or worklist integration with the local EHR will be permitted as a site specific IT decisions

Intellectual Property related to the Pieces TM platform is owned by the PCCI. Data definitions and workflows of the cohort selection will be public maintained and associated predictive models for specific aim three will be public released.

Dissemination Methods

Data Sharing Plan and Public Access

We are obliged to share our data within the analytic team of the ICD-Pieces TM trial. The authors will retain the rights to the deidentified final data until the trial is completed. Interested parties will be able to download information about the predictive model from the PCCI website.pccipieces.org.

Short term data storage of transfer files will occur via encrypted drives between password protected encrypted computers.

Roles and Responsibilities

PCCI data analyst

Software:

Statistical analysis planned perform in R Version, Stata MP version

MySQL Server 5.6

Pieces™ Platform Version 2.0

Deidentification Algorithm

DeID (Nematullah et al)

16. Study Administration

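### Confirmation and enrolment after unmasked randomisation are written mainly for the intervention arm, are not reconciled with the arm-neutral text, and leave a control patient's 12-month start without an operational definition

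*Combined protocol and SAP*

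**What the plan says.** **Text tied to the intervention arm.**

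- Section 5.4: "There will be no masking of sites randomized to active intervention".
- Section 6.4 has Pieces screen records, then randomises candidate sites, then says: "Within clinics randomized to intervention, Pieces will confirm patients meet inclusion criteria". It gives no matching sentence for control clinics.
- Section 7.2 describes the advance list and visit 1 for the intervention group. It makes visit 1 the first occasion on which the practitioner can initiate the study for a patient.
- Section 6.3: "A key component of the collaborative model of care for the intervention group is the introduction of practice facilitators". The facilitator's duties include activating enrolment and "In-person visit to observe processes of enrollment and Smart/Order set trigger and other intervention activities".
- Section 13.1: "The Practice Facilitator will receive the list of eligible patients along with their PCPs to ensure that the patients are enrolled into the study".
- Section 15.2 says that candidates with visits in the coming week "will be reported to the practice facilitator for additional follow up confirmatory testing to be arranged". That sentence names no arm.
- Section 6.5: "After a patient is enrolled, the primary care practitioner activates the CKD, diabetes and hypertension collaborative model of care".

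**Arm-neutral text.**

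- Section 7.1: "Potential study participants from each healthcare system followed in primary care clinics randomized to the study will be screened for inclusion". Patients who need a further determination to confirm a diagnosis are rescreened at a later visit.
- Section 15.2 stores snapshots of identification and confirmation data for all candidates and uses identical query logic on local copies of the data model.
- Section 4 includes all eligible patients of randomised practices in the intention-to-treat comparison.

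**The clock.** Section 7.4 counts 12 months from initiation of the study for the patient. Section 9.2.1, on adverse events, counts from enrolment, for each subject. Table 7.1 has a baseline visit with no arm named, but marks enrolment at every visit. Section 11 gives no index date.

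**The concern.** The primary outcome is a 12-month hospitalisation rate, and the Cox models in section 11.3 also need a time zero. Both require a rule that says who is in the analysis and when each patient's year begins, and the rule has to work in the same way in both arms.

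If the active steps run only in intervention clinics, two things can differ by arm. The first is who qualifies. Section 5.1.1 requires two or more abnormal kidney results at least 3 months apart, so a test arranged by a facilitator can complete eligibility for a patient whose control counterpart stays unconfirmed. Identical query logic does not prevent this, because the data that feed the query may have been generated differently. The second is when the year starts, because the only act tied to initiation is described for the intervention practitioner.

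The Mantel-Haenszel comparison adjusts for clustering and stratum but not for differential entry. The mixed model adjusts only for measured factors.

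**Working it through.** **Step 1: passages side by side.**

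| Step | Intervention clinic | Control clinic |
|---|---|---|
| Screening and rescreening | 7.1 | 7.1 |
| Confirmation | 6.4 | implied by rescreening in 7.1; no step written |
| Arranged confirmatory test | 15.2, through the facilitator | not stated; 15.2 names no arm, but 6.3 makes facilitators part of the intervention |
| Enrolment act | 6.3, 13.1 | not stated |
| Start of 12 months | 7.2 with 7.4, or 9.2.1 | 9.2.1 says enrolment; no act or date given |

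**Step 2: reproduce the plan's sample size.** Inputs from section 11.2: 14% against 11%, ICC 0.015, two-sided 5%, 80% power; 4,419, 4,738, 4,175 and 1,093 available patients in 25, 40, 50 and 9 clinics.

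- Unclustered n per arm = (1.960 + 0.842)² × (0.14×0.86 + 0.11×0.89) / 0.03² = 1,904, so 3,808 in total.
- Design effect per stratum = 1 + (m − 1) × 0.015. With m = 176.8, 118.5, 83.5 and 121.4 this gives 3.636, 2.762, 2.237 and 2.807; the patient-weighted mean is 2.881.
- 3,808 × 2.881 = 10,971. The pooled-variance version (1,907 per arm) gives 10,990. The plan states 10,991, so it reproduces.
- At the planned enrolled sizes (3,367, 3,610, 3,181 and 833) the mean design effect is 2.430.
- Effective N = 10,991 / 2.881 = 3,815, or 10,991 / 2.430 = 4,523.

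**Step 3: illustration of what could be at stake.** The share of intervention patients entering through arranged tests, and their risk, are not in the documents. Both are assumptions here, as is 1:1 allocation. Ranges cover the two design effects. SE = √[(pC(1−pC) + pI(1−pI)) / (effective N / 2)].

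(a) No true effect; arranged-test entrants have 9% risk against 14%. Spurious difference b = share × 5 points. False-positive rate = Φ(−1.96 + b/SE) + Φ(−1.96 − b/SE).

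(b) True 3-point effect; entrants have 1.25 times the 11% risk. The effect shrinks by share × 11 × 0.25 points. Power = Φ(effect/SE − 1.96).

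| Share | (a) Spurious difference, points | (a) False-positive rate | (b) Remaining effect, points | (b) Power |
|---|---|---|---|---|
| 0% | 0 | 5% | 3.00 | 80-86% |
| 5% | 0.25 | 5.6-5.7% | 2.86 | 76-83% |
| 10% | 0.50 | 7.3-7.8% | 2.73 | 72-79% |
| 20% | 1.00 | 14.8-16.6% | 2.45 | 62-69% |

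Example, (a) at 20%: 14% against 13%, SE = 0.01106 or 0.01016, giving 14.8% or 16.6%.

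**The case against.** The strongest reply is that the plan already treats the arms alike. Section 7.1 rescreens patients in all randomised clinics in order to confirm a diagnosis, and it cites the same patient-identification figure that section 6.4 cites. That figure is not shown and may contain a control workflow. Section 10.1 reviews the first 10 patients enrolled from every cluster. Section 5.3 gives participating systems advance notice of possible participants and tracks enrolment at every site. Section 6.7 can be read as placing facilitators in both groups, and section 7.3 captures outcomes with the same tools in both. Section 9.2.1 states a clock for each subject.

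Much of this stands. A reader might infer that control patients are never confirmed, or that they have no clock at all. The documents do not support either: section 6.4 does not say that control patients go unconfirmed, and a clock from enrolment is stated. What none of these passages supplies is the act or date that counts as enrolment in a control clinic.

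A reader might also infer that the comparison is biased in a known direction. That is not supported either. Patients found through arranged tests may be at lower or higher risk. Section 11.2 already counts 14,425 patients with the triad against 10,991 needed, and section 7.3 expects visits every 3 to 6 months, so repeat tests may arise in usual care too. Neither fact excludes differential entry, but neither suggests that it is large.

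**Conclusion.** The point holds as a should-fix. The readable text contains two sets of entry steps, one arm-neutral and one written for or routed through the intervention, and does not reconcile them. The event that starts the 12 months is not made operational for a control patient. This is more than missing detail: with a CKD criterion that needs two results at least 3 months apart, following the text as written can make entry to the primary analysis depend on arm.

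The conclusion rests on the text and not on the illustration. At an assumed 5% share the distortion is small; at 20% it is material; the true share, risk and direction are unknown. It also rests on what can be read, because the workflow figures are not shown. If both arms are in fact confirmed by the same query with a common start, most of the concern goes away, but the plan needs to say so.

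**What to change.** **Confirmation.** In 6.4, 7.1, 7.2 and 11.3, replace the restriction to intervention clinics with one automated EHR confirmation query, run identically and on the same schedule in control and intervention clinics. Define the primary analysis set by that query, whether or not the model of care is activated.

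**Time zero.** Define one index-date rule for both arms that does not depend on an act by the practitioner or facilitator. An example is the date on which the query is first met on or after a launch date common to both arms within each healthcare system. Use it in 7.4 and 9.2.1, for the 12-month primary outcome and in the Cox models.

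**Sensitivity and reporting.** A common query can still pick up tests arranged in one arm. Add a sensitivity analysis limited to patients who met all criteria on data recorded before launch, which arranged tests cannot affect. Report eligible and confirmed counts and baseline characteristics by arm.

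**Cost.** Changes to wording, one scheduled query and slightly more analysis; section 15.2 already stores the snapshots needed. Some intervention patients will have an index date before the model is activated, which slightly dilutes the effect. Patients confirmed after launch stay in the primary set, so the change does not by itself reduce the planned number.

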6.5 Implementation Collaborative Model of Care

The interventions selected for this pragmatic trial are supported by prior studies, clinical evidence and/or guidelines for treatment of CKD, diabetes and hypertension.^[5,25,24,65,67-71,31,34,11] Specific interventions include maintaining blood pressure less than 140/90mmHg, use of angiotensin-converting enzyme inhibitors (ACEI) or angiotensin receptor blockers (ARB), treatment with statins, aiming for hemoglobin A1C at the recommended target for coexisting

comorbidities, and avoiding nephrotoxic medications including non-steroidal anti-inflammatory drugs (NSAIDS). Other interventions will include education on CKD for both primary care providers and for patients using material prepared by NKDEP. Material on lifestyle modification and immunizations will also be included. (see figure 6.5.1)

After a patient is enrolled, the primary care practitioner activates the CKD, diabetes and hypertension collaborative model of care. The primary care practitioner will also have the option to activate smart forms already constructed and available from our team (see appendix section) from the electronic health record. Primary care practitioners will have the option to initiate protocols for CKD management, hypertension management, lipid and diabetes management. Protocols can be initiated via smartsets in the EHR. (see figures 6.5.2 *Initiation of Protocol from SmartSets and Links to SmartSets*). The specific and detailed protocols for hypertension management and diabetes/lipid management are included in appendices.

ICD-Pieces Patient Care Work Flow

[figure not shown]

Figure 6.5.1

Initiate Protocol from SmartSets

- From the SmartSet, the provider can place all 3 initiate orders at once, in a Future status

[figure not shown]

Figure 6.5.2 Initiation of Protocol from SmartSets

6.6 Maintenance of Provider and Facilitator Engagement

Engagement of primary care providers at the time of study initiation and throughout the entire duration will be focus of special attention by the study team. Educational materials on CKD, diabetes and hypertension will be provided to practitioners and facilitators. Materials developed by NKDEP are readily available for distribution to study sites. Primary care providers will be offered the opportunity to participate in continuing education (CME) provided as part of their participation in ICD-PIECES. In addition, efforts are underway to determine if it is possible to link active participation in the study with Quality Initiatives (QI) that could fulfill maintenance of certification (MOC) requirements.

As previously noted practice facilitators will be integrated into the study at all times including participation in the initial training curriculum, ongoing educational options and regularly scheduled study visits, conferences and reports.

6.7 Separation Control and Intervention Group

Several steps will be in place to maintain separation between groups and to assess fidelity to assigned regimen. First and foremost the selection of clinics/geographic clusters as unit of randomization for the study should reduce the risk of cross-contamination by completely separating not only providers but also facilitators, nurses, clerks and other professionals in the intervention groups from those in control groups.

We are aware that the healthcare systems in the study may at various times develop and bring for implementation competing initiatives and will review quarterly any new initiatives that the clinical leadership is planning across the healthcare systems. We will also work closely with the QI teams to be aware of any new initiatives that could overlap with ICD-PIECES. Our study team will also conduct quarterly reviews of any new national guidelines (from ASN, NKF, ADA) that could be relevant for the study population in ICD-PIECES. Any potential changes will be discussed with Steering Committee and reported to DSMB.

We are also planning to monitor the following as indirect measures of separation between implementation and control groups:

- Activation of Smart sets
- Referrals to educators (diabetes)
- Selection of education modules (for providers and for patients)
- Linkage to pharmacy (recommended medications)
- Immunization rates

A possible consequence of the facilitated protocol is increased utilization of health services and resources. We will monitor and compare utilization rates in control and intervention groups.

7. Study Schedule

